2.5.4 Windows for time points

The windows below will be employed for the main primary and secondary efficacy endpoints as well as vital sign which will also be collected during the study for both scheduled and unscheduled visits.

CGM

CGM values measured outside the visit window will be flagged for exclusion from analyses. No derivations of CGM endpoints will be performed for CGM data collected outside of the analysis CGM window. Study days for CGM evaluations are calculated from the randomization date, and Day 1 indicates the day of randomization.

	Target CGM visit in Study day	Analysis CGM window in study day
CGM study visit		
Week- 3 to Week -1	Day -20 to Day -1	-28 to -1
Week 10 to Week 12	Day 64 to 84	57 to 91

For 7-point SMPG, HbA1c, FPG and PROs: Day indicates days relative to randomization date, and Day 1 indicates the day of randomization.

7-point SMPG

	Target Study day	Analysis window in study day	
Time point			
Week 12	84	77 to 91	
HbA1c, FPG			
	Targeted Study Day	Analysis window in study days	
Time Point			
Week 12	84	77 to 91	

PROs

	Targeted Study Day	Analysis window in study days
Time Point		
Week 12	84	77 to 91

Vital signs - Safety

Study days for vital signs evaluations are calculated from the day of first IMP injection, the day of first IMP injection being Day 1. The last assessment before the first study drug intake will be considered as Baseline.

	Target visit in Study day	Analysis window in study day
Time Point		
Week 8	56	49 to 63
Week 12	84	77 to 91

One or more results for a required parameter may be recorded within a given visit window. In such an event, the assessment with the closest date to the scheduled visit date will be used. In the event of 2 observations within a given visit window being equidistant to the scheduled visit date, the first observation will be used for descriptive tabulations or figures.

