1.3 SCHEDULE OF ACTIVITIES (SOA)

	Screening (weeks)	F	Run-in	(weeks	Intervention period (weeks)														Follow up	Notes	
Procedure	-6/-5	-4	-3	-2	-1		1	2	3	4	5	6	7	8	9	10	11	12	EOTC	2 to 4 days after last IMP dose	Visit Windows: Site visits: ±3 days Phone call visits: ±1 day relative to Visit 6
Visit ^a	1	2	3	4 2	5 2	6	7 2	8	9	10	11	12 2	13 2	14	15	16 2	17 2	18 ^b		19 ^d	
Day	-42/-35	-28	-20	-14	-7	1	7	14	21	28	35	42	48	56	64	71	78	84		86-88	
Informed consent	Х																				To be repeated in case of rescreening
Inclusion/Exclusion criteria	Х	Х	Х			Х															
Demography	Х																				
Full physical examination including height and weight	Х																				
Medical history	Х																				Medical, surgical and diabetes history
Method of mealtime insulin titration	Х					х															Current method at screening and the one to be followed during treatment period at randomization
Vital signs and body weight	Х					х								Х				х	х		Vital signs include heart rate and blood pressure (sitting position)
Dispensation/collection of study diary		Χ	Х			Х								Х	Х			Х	Х		

	Screening (weeks)					lr	nterve	entio	n per	riod (v	veeks)				Follow up	Notes				
Procedure	-6/-5	-4	-3	-2	-1		1	2	3	4	5	6	7	8	9	10	11	12	EOT ^C	2 to 4 days after last IMP dose	Visit Windows: Site visits: ±3 days Phone call visits: ±1 day relative to Visit 6
Visit ^a	1	2	3	4 2	5 2	6	7 2	8	9	10 2	11	12 2	13	14	15	16 2	17 2	18 ^b		19 ^d	
Day	-42/-35	-28	-20	-14	-7	1	7	14	21	28	35	42	48	56	64	71	78	84		86-88	
Dispensation of study intervention						Х								Х							
IMP compliance check														Х				Х	х		Collecting and counting used and unused pens
IRT call ^e	Х					Х								Х				Х	Х		
Randomization						Х															
Documentation and review of basal and mealtime insulin dose	Х	Х	Х			х	Х	Х	Х	Х	Х	Х	Х	Х	Х	х	х	Х	х		
Prior and concomitant medication	Х	Х	Х			Х					и			Х				Х	Х	Х	
CGM device dispensation ; blinded CGM and training including insertion of CGM sensor			X												х				х		If required, Investigators can arrange for patient's to attend the site after the first 10 days of CGM for the sensor to be replaced at the study site.
CGM recording ^f				20days											2	20 days	s	Х			

	Screening (weeks)	I	Run-in	(weeks	s)					lr	nterve	entio	n per	riod (v	veeks	s)				Follow up	Notes
Procedure	-6/-5	-4	-3	-2	-1		1	2	3	4	5	6	7	8	9	10	11	12	EOTC	2 to 4 days after last IMP dose	Visit Windows: Site visits: ±3 days Phone call visits: ±1 day relative to Visit 6

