- a Telephone calls to monitor insulin titration should be scheduled by the Investigator for Weekly in between of site visits for all patients, unless the patient is attending the study site for sensor replacement. Option to come to site on D-10 and D74 for sensor replacement.
- b Visit 18 will occur at Week 12 regardless of the treatment end date, and procedures ticked below should be done
- c EOT (End Of Treatment) visit will occur in case of premature discontinuation of study treatment before Visit 18 at week 12 and related procedures ticked below should be applied. If at the time of such premature discontinuation there is ongoing CGM recording, it should be completed, and EoT vist done thereafter. Afterward, the patients should continue in the study up to the scheduled date of study completion. See Section 7.1
- d If EOT visit occurs beyond 2 to 4 days after last administration of study drug then Visit 8 will not be required. EOT and safety follow up can be done at the same time, if occurs within 2 to 4 days after last IMP dose.
- e The Investigator should contact IRT either at Visit 18 or at EOT visit in case of premature end of treatment (whichever occurs first), to register end of treatment.
- f For each 20 day CGM period to be fully evaluable for CGM it is necessary to obtain a minimum of 10 days (not necessarily consecutive) of useable CGM data. Useable CGM data for a day/a 24-hour CGM profile are defined as: at least 80% time of records per 24 hours; no gap (missing data) lasting for ≥2 hours per 24 hours besides the warm-up time for the sensor after insertion.
- g SMPG to be performed by the patients from run-in period and throughout the study duration:
 - 1. Fasting (pre-breakfast/pre-injection) SMPG: daily until dose stabilization of basal insulin has been completed and fasting SMPG goal is reached. Thereafter, the number of fasting SMPG checks can be reduced according to the Investigator's judgment, however at least 3 fasting (pre-breakfast) SMPG measurements per week should be done.
 - 2. SMPG values throughout the study, starting after Visit 2. Patients should test their SMPG following the Investigator's instructions for mealtime insulin titration.
 - 3. 2hPPG (post prandial plasma glucose); regularly as instructed by investigator to guide meal time insulin titration;

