Before (pre-injection after randomization) and 2 hours after breakfast; lunch; dinner, and at bedtime: at least 1 day during the week that precedes Visits 6 and 18. Note: 7-point SMPG profile should also be pre-injection during the run-in period in cases where the patient's current basal insulin is administered in the morning.

SMPG during symptomatic hypoglycemia

Whenever the patients feel hypoglycemic symptoms, plasma glucose should be measured by the patient (or others, if applicable), if possible. Patients should be instructed to self-assess plasma glucose levels prior to carbohydrate intake/administration of glucose whenever symptomatic hypoglycemia is suspected, unless safety considerations necessitate immediate carbohydrate/glucose rescue prior to confirmation with the SMPG.

Patients have to document hypoglycemic events appropriately in their diaries and contact the Investigator as soon as possible following severe events for review and for decision on any necessary actions to be taken.

All hypoglycemia episodes will be documented on the "hypoglycemia specific form" in the eCRF. This includes all symptomatic hypoglycemia events and asymptomatic hypoglycemia. Investigators should review the SMPG diary entries (and when available also data stored in the glucometer) to assess data for episodes of hypoglycemia, ie, to confirm episodes reported by patients in the diary and also to identify any episodes that were not reported in the diary).

Property of the Sanofi group - strictly confidential

Page 49

Hypoglycemia events fulfilling the criteria of a SAE will also be documented on the AE and SAE form in the eCRF.

Recording of SMPG data

Patients will document their SMPG values with the testing times in the Sponsor-provided diary. If for any reason, SMPG is recorded by the patient in a non-Sponsor provided diary, the Investigator (or designee) and patient will sign/initial the data so that the diary can be kept in the study source documents.

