At on-site Visits 6, 14, and 18, SMPG data stored in the individual's glucometer will be uploaded to the site's computer. A summary including all measured glucose values will be promptly available for the Investigator (or designee) to review. SMPG data will be uploaded to site's PC (server independent from eCRF). At a minimum, for SMPG data that are captured in the eCRF, including the values recorded during weekly telephone contacts, the Investigators or study staff must verify the accuracy with the data that are uploaded from the glucometer. Once an error is identified, only the corrected data should be entered in the eCRF and erroneous data in the diary will be corrected by the patient and initialed.

Use of SMPG data for future analysis

The SMPG data from the glucometer will be uploaded to an independent server and will not be captured in the clinical database (which will comprise SMPG data that is transcribed from the study diary).

The downloaded SMPG data will not be analyzed or reported in the clinical study report.

After the database lock anonymized SMPG data may be transferred to third party for future analysis and modeling of glycemic values.

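### The SAP's Week 12 window for the 7-point SMPG profile (Day 77 to 91) leaves out days the protocol allows when Visit 18 is early, if the window is applied to the measurement date

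*SAP*

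**What the plan says.** SAP 2.5.4 (Windows for time points) has a separate table for the 7-point SMPG profile. The Week 12 target is Day 84 and the analysis window is Day 77 to 91. HbA1c, FPG and the PROs have the same target and window. The day count for all of them is fixed by one sentence: "For 7-point SMPG, HbA1c, FPG and PROs: Day indicates days relative to randomization date", with randomization itself counted as Day 1.

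Protocol 8.1.4 places the 7-point profile "at least 1 day during the week that precedes Visits 6 and 18". The footnote on SMPG in the schedule of activities (Protocol 1.3) says the same.

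The schedule puts Visit 18 at Day 84 and states the tolerance as "Site visits: ±3 days Phone call visits: ±1 day relative to Visit 6". Visit 18 is a site visit: Protocol 8.1.4 names it among those at which the glucometer is uploaded ("At on-site Visits 6, 14, and 18"). The ±3 days therefore apply to it.

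**The concern.** The profile is collected over the week before the visit, and the visit itself can move by 3 days in either direction. The SAP window treats the profile as if it were taken at the visit, like HbA1c, FPG and the PROs. Its lower limit, Day 77, is the first day of the preceding week only when Visit 18 falls exactly on Day 84, so there is no room for an early visit.

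At stake is the completeness of the Week 12 profile and its change from baseline. A patient who attends early but within tolerance, and who does the one profile that the protocol requires as a minimum, could have no Week 12 value.

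**Working it through.** **Inputs**
- SAP window for the 7-point profile: Day 77 to 91, target Day 84 (SAP 2.5.4).
- Day 1 is the day of randomization (SAP 2.5.4). The protocol schedule also has Visit 6, the randomization visit, on Day 1, so both documents count from the same day.
- Visit 18: Day 84 ± 3 (Protocol 1.3), so the visit day v runs from 81 to 87.
- Allowed profile days: the week before Visit 18 (Protocol 8.1.4), taken as v − 7 to v − 1.

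**The SAP's own figure.** 84 − 7 = 77 and 84 + 7 = 91. The window is the target day ± 7.

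**Allowed days against the window**

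| Visit 18 on Day | Allowed profile days | Outside 77 to 91 | Share |
|---|---|---|---|
| 81 | 74 to 80 | 74, 75, 76 | 3/7 = 43% |
| 82 | 75 to 81 | 75, 76 | 2/7 = 29% |
| 83 | 76 to 82 | 76 | 1/7 = 14% |
| 84 | 77 to 83 | none | 0 |
| 85 | 78 to 84 | none | 0 |
| 86 | 79 to 85 | none | 0 |
| 87 | 80 to 86 | none | 0 |

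The earliest compliant day is 84 − 3 − 7 = 74, which is 3 days before the window opens. The latest is 84 + 3 − 1 = 86, which is 5 days before it closes. The slack is all at the upper end.

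**Overall share.** There are 7 × 7 = 49 combinations of visit day and profile day, and 3 + 2 + 1 = 6 fall outside: 6/49 = 12.2%. This is a rate of loss only if visit days are uniform over Day 81 to 87, profile days are uniform over the preceding week, and each patient has one profile. If visits are kept to Day 83 to 85, the same count gives 1/21 = 4.8%. The documents give no distribution for either day.

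**If the preceding week is read as including the visit day** (v − 6 to v), the days outside are 75 and 76 for Visit 18 on Day 81 (2/7), 76 for Day 82 (1/7), and none from Day 83: 3 of 49. The conflict shrinks but remains.

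**Comparison with the other windows.** CGM is also collected over several days. Its target is a range, Day 64 to 84, and the window adds 7 days at each end (64 − 7 = 57, 84 + 7 = 91). The profile has a single target day instead. HbA1c, FPG and the PROs are taken at Visit 18 itself (Day 81 to 87), which lies wholly within Day 77 to 91.

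**After the change.** With Day 74 to 91, 0 of the 49 combinations fall outside. With Visit 18 minus 7 days through Visit 18, none do either.

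**The case against.** The day arithmetic is hard to dispute. The case on the other side concerns whether profiles would really be lost, and how much it matters.

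- **Exclusion is inferred.** The sentence in SAP 2.5.4 that excludes out-of-window values is written for CGM only. The opening sentence of the section ("The windows below will be employed for the main primary and secondary efficacy endpoints as well as vital sign") does not name exploratory endpoints. This stands as a limit on certainty. Yet the profile has its own window table, which serves no purpose unless it decides what counts as Week 12, and no SAP text provides for a profile before Day 77.
- **The dating convention is not stated.** The target is the planned Visit 18 day, and the schedule of activities ticks the profile under Visit 18. If profiles are dated by the visit, Day 81 to 87 is always inside the window and nothing is lost. The documents do not settle this. The rule for several results in one window chooses by the date of the assessment, which points toward the measurement date without proving it.
- **More than one profile is possible.** The protocol sets one day as a minimum. A patient with a second profile on Day 77 or later is retained. This stands.
- **The endpoint carries little weight.** It is tertiary/exploratory in Protocol Table 1 and SAP 2.1.3.3, is summarized by mean and SD, and has no place in the testing hierarchy. This stands.

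A reader might infer that compliant profiles will certainly be discarded, or that about 12% of Week 12 profiles will go missing. The documents support neither. The first depends on the unstated dating convention and on no later profile being available; the second depends on uniform days that no text supplies. Nor does anything in the documents suggest that a loss would differ between the arms.

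**Conclusion.** The two documents do not fit together on this point, but the consequence is conditional and minor. A compliant profile is left out only if three things hold: the window is applied to the measurement date, Visit 18 falls on Day 81 to 83, and the patient has no profile on Day 77 or later. Under those conditions the share of allowed days rejected is 43%, 29% or 14% by visit day, and zero from Day 84. The trial-wide loss is unknown; the 12% is an illustration and should not be quoted as an estimate. The result affected is a descriptive table and figure. The primary endpoint, power and type I error are untouched.

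**What to change.** Before database lock, change the Week 12 analysis window for the 7-point SMPG profile in SAP 2.5.4 to Day 74 to 91. Alternatively, define it relative to the actual visit, as Visit 18 minus 7 days through Visit 18. In the same place, state that the window applies to the date of measurement. Leave the HbA1c, FPG and PRO windows unchanged.

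If the visit-relative form is chosen, it must start at Visit 18 minus 7. A seven-day window that ends on and includes the visit day would begin at Visit 18 minus 6 and drop the first allowed day for every patient. That is 1 of 7 allowed days (14%) whatever the visit date, including visits on Day 84 to 87, which lose nothing under the present window.

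The cost is one table cell and one clarifying sentence, with no change to data collection or to any other analysis.

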2.5.5 Unscheduled visits

Unscheduled visit measurements of vital signs will not be included in the by-visit summaries but will be used for computation of baseline and analysis visit definition.

2.5.6 Pooling of centers for statistical analyses

No pooling of centers is planned for statistical analyses: center and country will not be included in statistical analysis.

2.5.7 Statistical technical issues

Not applicable for the study.

01-Jul-2021 Version number: 1

3 INTERIM ANALYSIS

No interim analysis is planned.

01-Jul-2021 Version number: 1

4 DATABASE LOCK

The database is planned to be locked 4 weeks after last patient last visit.

7 LIST OF APPENDICES

Appendix A: Summary of statistical analyses

Appendix B: Questionnaires (PROs)

APPENDIX A: SUMMARY OF STATISTICAL ANALYSES

EFFICACY ANALYSIS

Endpoint	Analysis population	Primary analysis	Supportive analysis	Subgroup analysis	Other analyses
Primary endpoint					
Percent of time in glucose range of ≥70 to ≤180 mg/dL (≥3.9 to ≤10 mmol/L) using continuous glucose monitoring (CGM) at Week 12	ITT, PP, ITT COVID 19 free	For ITT population: ANCOVA with fixed categorical effects Trt and randomization stratum HbA1c and continuous fixed covariate of baseline percent in range value with multiple imputation of missing data Non inferiority with a relative non- inferiority margin of 10 % is the primary analysis	1st Sensitivity analyses: same modeling (ANCOVA) with MI on PP population 2nd Sensitivity analyses same modeling (ANCOVA) with multiple imputation of missing data being imputed in conjunction with MNAR assumption from ITT population. 3rd sensitivity analyses: same	Yes, subgroup by screening and baseline factors such as duration of diabetes, Gender, Randomization strata, BMI.	In addition to the non-inferiority testing that is the primary analysis, and only if non-inferiority of Toujeo in comparison to Tresiba on the percent time in the range of 70-180 mg/dL is demonstrated and if non-inferiority of Toujeo versus Tresiba on the glucose total CV is demonstrated, superiority of Toujeo over Tresiba on the percent time in the range of 70-180 mg/dL will be tested
			modeling (ANCOVA) with MI on Population without trial impact		
			(disruption) due to COVID-19		

Statistical Analysis Plan HOE901-U300-LPS14947		01-Jul Versio)1-Jul-2021 /ersion number: 1		
Endpoint	Analysis population	Primary analysis	Supportive analysis	Subgroup analysis	Other analyses
Secondary endpoints					
Glucose total CV using CGM at Week 12 (Main secondary endpoint)	ITT	ANCOVA model to perform the analysis includes the fixed categorical effects of treatment group (Toujeo, Tresiba),and randomization stratum of screening HbA1c (<8.0%versus ≥8.0%), as well as, the continuous fixed covariate of baseline value for the corresponding endpoint As this is the main secondary endpoint: Multiple imputation (as for primary endpoint) and non-inferiority with a relative non-inferiority margin of 10 % tested in case of non-inferiority demonstrated for primary analysis of primary endpoint	No	No	No
Glucose within-day CV using CGM at Week 12	ITT	The ANCOVA model to perform the analysis includes the fixed categorical effects of treatment group (Toujeo, Tresiba), and randomization stratum of screening HbA1c (<8.0%versus ≥8.0%), as well as, the continuous fixed covariate of baseline value for the corresponding endpoint.	No	Yes, subgroup defined by glucose within day CV ≤36% vs. >36% at baseline.	No
Glucose between-day CV using CGM at Week 12	ITT	The ANCOVA model to perform the analysis includes the fixed categorical effects of treatment group (Toujeo, Tresiba), randomization stratum of screening HbA1c (<8.0%versus ≥8.0%), as well as, the continuous	No	No	No

01-Jul-2021 Version number: 1

Endpoint	Analysis population	Primary analysis	Supportive analysis	Subgroup analysis	Other analyses
		fixed covariate of baseline value for the corresponding endpoint.	-		
HbA1c Change from baseline at Week 12	ITT	Change in HbA1c will be analyzed using an ANCOVA model including the fixed categorical effects of treatment group (Toujeo, Tresiba), as well as, the continuous fixed covariate of baseline HbA1c value.	No	No	No
		95% CI and P-values presented for these endpoints will be done for descriptive purposes only.			
FPG Change from baseline at Week 12	ITT	Change in FPG will be analyzed using ANCOVA model including the fixed categorical effects of treatment group (Toujeo, Tresiba), and the randomization stratum of HbA1c at screening (<8.0%, ≥8.0%), as well as, the continuous fixed covariate of baseline FPG value.	No	No	No
		95% CI and P-values presented for these endpoints will be done for descriptive purposes only.			
Tertiary/exploratory er	ndpoints excep	ot PROs			
Change from baseline in 7- point SMPG profiles (pre- prandial and 2-hour postprandial plasma glucose at breakfast, lunch and dinner, and at bedtime) to Week 12	ITT	Descriptive summary statistics by treatment group	No	No	No

Endpoint	Analysis population	Primary analysis	Supportive analysis	Subgroup analysis	Other analyses
Mean hours per day in the CGM glucose range of ≥70 to ≤180 mg/dL (≥3.9 to ≤10 mmol/L)	ITT	Descriptive summary statistics by treatment group	No	No	No
Percent time and mean hours per day in the CGM glucose range of \geq 70 to \leq 140 mg/dL (\geq 3.9 to \leq 7.8 mmol/L) (for all-time and during the night [00:00 to 05:59])	ITT	Descriptive summary statistics by treatment group	No	No	No
Nocturnal percent time in CGM glucose range of ≥70 to ≤180 mg/dL (≥3.9 to ≤10 mmol/L) at Week 12, obtained using CGM	ITT	Descriptive summary statistics by treatment group	No	No	No
Percent time and mean hours per day with CGM glucose: <54 mg/dL, (for all time and during the night [00:00 to 05:59])	ITT	Descriptive summary statistics by treatment group	No	No	No
Percent time with CGM glucose <70 mg/dL within the 12 hours after basal insulin injection	ITT	Descriptive summary statistics by treatment group	No	No	No
Percent time and mean hours per day with CGM glucose >250 mg/dL	ITT	Descriptive summary statistics by treatment group	No	No	No
Mean CGM glucose profile over 24-hour period	ITT	Graphic presentation	No	No	No

Statistical Analysis Plan HOE901-U300-LPS14947

01-Jul-2021 Version number: 1

Endpoint	Analysis population	Primary analysis	Supportive analysis	Subgroup analysis	Other analyses
24h-AUC of CGM glucose values	ITT	Descriptive summary statistics by treatment group	No	No	No
Mean glucose	ITT	Descriptive summary statistics by treatment group	No	No	No
GMI	ITT	Descriptive summary statistics by treatment group	No	No	No
Percent time and mean hours per day in the CGM glucose range of ≥54 to <70 mg/dL (for all-time and during the night [00:00 to 05:59]),	ITT	Descriptive summary statistics by treatment group	No	No	No
Percent time and mean hours per day in the glucose range of ≥180 to <250 mg/dL (on all-time and during the night [00:00 to 05:59]),	ITT	Descriptive summary statistics by treatment group	No	No	No
Daily insulin doses (total daily insulin, total basal insulin, total mealtime insulin, ratio of basal to mealtime insulin dose) in units and U/kg body weight	Safety	Descriptive summary statistics (including change from baseline to Week 12) by treatment group	No	No	No
PROs endpoints					
DTSQs	ITT	Change in DTSQs scores from baseline to Week 12 will be analyzed using an analysis of covariance (ANCOVA) model including the fixed categorical effects of treatment group (Toujeo, Tresiba), and the	No	No	No

01-Jul-2021 Version number: 1

Endpoint	Analysis population	Primary analysis	Supportive analysis	Subgroup analysis	Other analyses
		randomization stratum of HbA1c at screening (< 8.0% , $\geq 8.0\%$), as well as, the continuous fixed covariate of baseline score.			
		LS means and its corresponding 95% confidence interval by treatment for the change from baseline will be presented for descriptive purposes			
DTSQc	ITT	The DTSQc scores at Week 12 will be analyzed using an analysis of covariance (ANCOVA) model including the fixed categorical effects of treatment group (Toujeo, Tresiba),and the randomization stratum of HbA1c at screening (<8.0%, \geq 8.0%).	No	No	No
		LS means and its corresponding 95% confidence interval by treatment for the change from baseline will be presented for descriptive purposes			
MOS Sleep	ITT	Change in MOS-Sleep from baseline to Week 12 will be analyzed using an analysis of covariance (ANCOVA) model including the fixed categorical effects of treatment group (Toujeo, Tresiba), and the randomization stratum of HbA1c at screening (<8.0%, ≥8.0%), as well as, the continuous fixed covariate of baseline score.	No	No	No
		LS means and its corresponding 95% confidence interval by treatment for the change from baseline will be presented for descriptive purposes			

01-Jul-2021 Version number: 1

Endpoint	Analysis population	Primary analysis	Supportive analysis	Subgroup analysis	Other analyses	
WPAI	ITT	Change in WPAI scores from baseline to Week 12 will be analyzed using an analysis of covariance (ANCOVA) model including the fixed categorical effects of treatment group (Toujeo, Tresiba), and the randomization stratum of HbA1c at screening (<8.0%, ≥8.0%), as well as, the continuous fixed covariate of baseline score LS means and its corresponding 95% confidence interval by treatment for the change from baseline will be presented for descriptive purposes	No	No	No	

ANCOVA = analysis of covariance; ITT = intent-to-treat; PP = per-protocol

SAFETY ANALYSES

Endpoint	Analysis population	Primary analysis	Supportive analysis	Subgroup analysis	Other analyses
Number of patients with adverse events	Safety	Summary by treatment group using number and % of patients experiencing at least one adverse event, focusing on TEAE	No	No	No
Number of patients with at least one hypoglycemic event from baseline to Week 12	Safety	Summary by treatment group using number and % of patients experiencing at least one hypoglycemic event will be presented for any hypoglycemia and for each type of hypoglycemia, overall and according to time of occurrence (nocturnal [ie, 00:00 to 05:59], any time of day and daytime [ie, 06:00 to	No	No	No

Statistical Analysis Plan
HOE901-U300-LPS14947

Endpoint	Analysis population	Primary analysis	Supportive analysis	Subgroup analysis	Other analyses	
		23:59] during the 12-week on treatment period				
		Logistic regression model adjusted on randomization strata of screening HbA1c to estimate Odds Ratio and its corresponding 95% CI for the Toujeo arm over the Tresiba arm for each hypoglycemic event				
Number of hypoglycemic events per participant-year from baseline to Week 12	Safety	Number and rate of hypoglycemic events (in patient-year of exposure) will be determined for any hypoglycemia and for each type of hypoglycemic event, overall and according to time of occurrence (nocturnal [ie, 00:00 to 05:59], any time of the day) during the 12-week on treatment period. Over-dispersed Poisson regression model adjusted on randomization strata of screening HbA1c to estimate for each hypoglycemic event, the rate ratio, and its corresponding 95% CI, of Toujeo arm over Tresiba arm	No	No	No	

01-Jul-2021 Version number: 1

